# 13.9 Exploratory/Correlative Analysis

The additional correlative analyses will be primarily descriptive in nature. Plots (e.g. histograms, scatter and spaghetti plots) and summary statistics (medians, ranges, counts, proportions) will be used to summarize patterns over time and compare outcomes. Comparisons in the pre- and post-treatment responses will be compared using paired ttests (or Wilcoxon signed rank tests if appropriate) for continuous variables and McNemar's tests for dichotomous or categorical variables. Peripheral blood samples will be analyzed for ctDNA, CTCs and  $\gamma$ H2AX foci in CTCs at serial time points during the study in order to identify therapeutic targets, biomarkers, and predictors of response. Additionally, urine samples will be analyzed for F2-isoprostane and 8-oxo-2'-deoxyguanosine levels at serial time points during the study in order to identify the impact of study therapy on oxidative toxicities, which will be correlated to therapeutic outcomes.

Genomic sequencing library construction, whole genome/exome sequencing, whole transcriptome sequencing, microbial sequencing, neoepitope prediction, mutation burden, and bioinformatic analysis will be performed either at an on-campus laboratory or at an off-campus sequencing service. All the samples will be de-identified before sending to any laboratory for sequencing. The FASTQ files, BAM files and VCF files will be generated and analyzed. Genomic sequencing data will be stored and computations conducted using a JH IT managed subscription of Azure.

Results from the sequencing studies will not be released to the patients. These studies are for research purposes only and are not using a clinically validated platform

**APPENDIX A: Performance Status Criteria** 

ECOG Pe	ECOG Performance Status Scale		Karnofsky Performance Scale			
Grade	Descriptions	Percent	Description			
	Normal activity. Fully active, able to carry on all	100	Normal, no complaints, no evidence of disease.			
0	pre-disease performance without restriction.	90	Able to carry on normal activity; minor signs or symptoms of disease.			
1	Symptoms, but ambulatory. Restricted in physically strenuous activity, but ambulatory and able to	80	Normal activity with effort; some signs or symptoms of disease.			
1	carry out work of a light or sedentary nature (e.g., light housework, office work).	70	Cares for self, unable to carry on normal activity or to do active work.			
2	In bed <50% of the time. Ambulatory and capable of all self-care, but unable to carry out any work	60	Requires occasional assistance, but is able to care for most of his/her needs.			
	activities. Up and about more than 50% of waking hours.	50	Requires considerable assistance and frequent medical care.			
_	In bed >50% of the time. Capable of only limited self-	40	Disabled, requires special care and assistance.			
3	care, confined to bed or chair more than 50% of waking hours.	30	Severely disabled, hospitalization indicated. Death not imminent.			
4	100% bedridden. Completely disabled. Cannot carry on any self-	20	Very sick, hospitalization indicated. Death not imminent.			
	care. Totally confined to bed or chair.	10	Moribund, fatal processes progressing rapidly.			
5	Dead.	0	Dead.			

# **APPENDIX B: Serious Adverse Event Reporting Form**

Please notify: [name] within 24 hours (email: [contact]) Monitor/[name] within 24 hours (emails: [contact], [contact])

AstraZeneca within 24 hours (email: [contact]; [contact]) McGuff within 24 hours (email: [contact]

Protocol Title:	Phase II Study of PARP Inhibitor Olaparib and IV Ascorbate in Metastatic						
	Castration Resistant Prostate Cancer						
Protocol Number:	Signat	ure of PI:	Principal Investigator: [name]		Date of Report:		
Report Type:  Initial Follow-up Final Follow-up	Serious Criteria (check all that apply):  Death Life-threatening Hospitalization or Elongation of Existing Hospitalization Other Important Medical Event Cancer Overdose Other:		Hospital Admission Date:		Date Event Discovered:		
□Death □Addendum to:			Hospital Discharge Date:		SAE ID:		
Section A: Subject In	nforma	tion					
Subject ID:	Subject Gender ☐ Male ☐ Female	∵:	Subject A	ge:			
Section B: Event Inf	ormati						
Event diagnosis or symptoms:		Event Grade:	Cause of death (if applicable):		vent Outcome:  Not Recovered Recovered Recovered Recovered with equelae Death Unknown		
Event Onset Date (or Date of Death):			Event End Date:				
Section C: Study Drug Information							
Investigational Pro Olaparib 300 mg BID IV Ascorbic Acid (1 g	duct: /kg, 2x						
muication: castratio	ni kesis	tant Frostate Gancer (CRPC)					

Number of Total Cy	☐ None ☐ Interru ☐ Delaye	Action taken with the study drug:  None Interrupted Delayed Discontinued						
Date of First Dose:	D	Date of Last Dose prior to Event:						
Relationship to:	Ol	aparib		IV Ascorb	oic Acid	Underlying Disease		
Unrelated		 					Π	
Related								
Section D: Brief Des	scription of th	ne Event:						
Section E: Relevant Tests/Laboratory Data								
Section F: Relevant Medical History								
occurrent Program Indian								
Section G: Concomi	tant Drug (No	ot related to	SAE)					
Name of the Drug			t Date	Stop Date	Route	Dose	Frequency	
Section H: Comments								
Additional Documents: Please specify								

## **APPENDIX C: Contraception**

Olaparib is regarded as a compound with medium/high fetal risk. Subjects with partners of childbearing potential, who are sexually active, must agree to the use of TWO highly effective forms of contraception in combination [as listed below], throughout the period of taking study treatment and for at least 1 month after last dose of study drug(s), or they must totally/truly abstain from any form of sexual intercourse (see below).

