#### 5.0 PATIENT SELECTION

# 5.1 Inclusion Criteria

Patients are eligible to be included in the study only if they meet *all* of the following criteria:

- [1] Have metastatic castration-resistant prostate cancer (prostate cancer progressing by PSA (rise by 25% on prior therapy) or imaging despite castrate levels of testosterone [<50 ng/dL] using standard measures of progression defined by Prostate Cancer Working Group).
- [2] Have a minimum PSA of 1 ng/mL.
- [3] Have a pathological diagnosis of prostate carcinoma.
- [4] Have been receiving and will continue to receive continuous hormonal ablation with surgical or medical castration with baseline testosterone <50ng/dL.
- [5] May be receiving bone-targeted agents.
- [6] May have received multiple lines of therapy including radium 223, sipuleucel T, and up to 2 lines of chemotherapy (One of 2 lines may be for hormone sensitive metastatic prostate cancer or both can be for castration resistant).
- [7] Age  $\geq$  18.
- [8] Have ECOG performance status 0-1 (Appendix A).
- [9] Be able to take oral medication and willing to consider a port for ease of administration of ascorbate.
- [10] Must have progressed on one systemic line of treatment (can include LHRH agonist/antagonist or orchiectomy and at least one additional line of therapy (abiraterone, enzalutamide, apalutamide, darolutamide, docetaxel, etc)).
- [11] Have normal organ and marrow function measured within 28 days prior to administration of study treatment as defined below:

- Absolute neutrophil count  $>1.5 \times 10^9/L$ -Platelets  $> 100,000/mm^3$ 

-Hemoglobin > 9g/dL with no blood transfusion in the

past 28 days

-Total bilirubin < 1.5 x ULN

-AST (SGOT)/ALT(SGPT)  $\leq$  2.5 x ULN (<5x ULN if with known liver

metastases provided bilirubin is normal

-Creatinine  $\leq$  1.6 x ULN (for patients with  $\geq$  1.6 x ULN, calculated

or measured creatinine clearance must be > 60

mL/minute (Cockcroft-Gault).

- [12] Men of reproductive potential and those who are surgically sterilized (i.e. post-vasectomy) must agree to practice effective barrier contraception that has an expected failure rate of <1% during and for 6 months after discontinuation of study treatment. Female partners should also use a highly effective form of contraception ([see **Appendix C** for acceptable methods]) if they are of childbearing potential.

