# 7.8 Contraception

Male patients must use a condom during treatment and for 3 months after the last dose of olaparib when having sexual intercourse with a pregnant woman or with a woman of childbearing potential. Female partners of male patients should also use a highly effective form of contraception (as described in **Appendix C**) if they are of childbearing potential. Male patients should not donate sperm throughout the period of taking olaparib and for 3 months following the last dose of olaparib.

For details of acceptable methods of contraception refer to **Appendix C** Acceptable Birth Control Methods.

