#### 9.1.6 Pregnancy

Male participants should refrain from fathering a child or donating sperm during the study and for 3 months following the last dose.

Pregnancy of the patient's partners is not considered to be an adverse event. However, the outcome of all pregnancies (spontaneous miscarriage, elective termination, ectopic pregnancy, normal birth or congenital abnormality) should if possible be followed up and documented.

The outcome of any conception occurring from the date of the first dose until 3 months *after the last dose* should be followed up and documented.

All outcomes of pregnancy should be reported to AstraZeneca and McGuff.

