## Acceptable Non-hormonal birth control methods include:

- Total sexual abstinence. Abstinence must continue for the total duration of study treatment and for three months after the last dose for male patients. Periodic abstinence (e.g. calendar ovulation, sympothermal, post ovulation methods) and withdrawal are not acceptable methods of contraception.
- Vasectomised sexual partner PLUS male condom with participant assurance that partner received post-vasectomy confirmation of azoospermia.
- Tubal occlusion PLUS male condom
- IUD PLUS male condom. Provided coils are copper-banded

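### The protocol gives three different minimum contraception periods after treatment (6 months, 3 months, at least 1 month), counted from differently worded starting points, and its conception follow-up window matches only one of them

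*Combined protocol and SAP*

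**What the plan says.** Five statements set a period after treatment for the male patient.

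- Section 5.1, criterion 12: men of reproductive potential, and men who have been surgically sterilised, must agree to effective barrier contraception "during and for 6 months after discontinuation of study treatment".
- Section 7.8: "Male patients must use a condom during treatment and for 3 months after the last dose of olaparib", when the partner is pregnant or of childbearing potential. Sperm donation is barred "for 3 months following the last dose of olaparib".
- Section 9.1.6: "Male participants should refrain from fathering a child or donating sperm during the study and for 3 months following the last dose".
- Appendix C, opening paragraph: sexually active subjects with partners of childbearing potential must use two highly effective forms together during treatment and "for at least 1 month after last dose of study drug(s"), or abstain.
- Appendix C, list of non-hormonal methods: "Abstinence must continue for the total duration of study treatment and for three months after the last dose for male patients".

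On pregnancy follow-up, Section 9.1.6 has a sentence beginning "The outcome of any conception occurring from the date of the first dose until 3 months" after the last dose, which limits the window for documenting outcomes. The text on either side of that sentence asks for the outcome of all pregnancies to be followed if possible, and for all outcomes to go to the two drug suppliers. The participating-sites part of Section 9.5.1 requires every pregnancy of a patient's partner to be followed to its end. Neither of these gives a 3-month limit.

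**The concern.** All five statements are in current operative text, and they govern the same safeguard in the same patients. Appendix C itself places olaparib in the medium-to-high range for fetal risk, so the length of the safeguard matters for partners and any pregnancy. In a multi-center trial, staff who take the duration from different sections would give different instructions, and adherence to the commitment made under criterion 12 could not be judged against a single standard. The conception window raises a second question: whether a pregnancy conceived after month 3, but within the 6 months agreed at entry, must be documented.

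**Working it through.** There is no statistical figure to reproduce. The check sets the statements side by side.

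| Place | Measure | Minimum after treatment | Counted from |
|---|---|---|---|
| 5.1, criterion 12 | Barrier contraception | 6 months | Discontinuation of study treatment |
| 7.8 | Condom; no sperm donation | 3 months | Last dose of olaparib |
| 9.1.6 | No fathering or sperm donation | 3 months | Last dose (drug not named) |
| Appendix C, opening | Two methods combined | At least 1 month | Last dose of study drug(s) |
| Appendix C, abstinence line | Abstinence | 3 months | Last dose (drug not named) |
| 9.1.6, conception window | Outcome documented | 3 months | Last dose (drug not named) |

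**Differences between the stated minimums**

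- 3 − 1 = 2 months (Sections 7.8 and 9.1.6 against the opening of Appendix C).
- 6 − 3 = 3 months (Section 5.1 against Sections 7.8 and 9.1.6).
- 6 − 1 = 5 months (Section 5.1 against the opening of Appendix C).

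The shortest minimum is therefore 2 to 5 months below the others.

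**Do the statements concern the same measure?** They are worded differently, but they overlap. Apart from abstinence, every method listed in Appendix C includes a male condom. The 1-month minimum therefore applies to the condom that Section 7.8 requires for 3 months, and to a barrier method of the kind criterion 12 requires for 6. Appendix C also disagrees with itself: at least 1 month for two methods in combination, but 3 months for abstinence, which its opening paragraph offers as the alternative.

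**Can the starting points differ in practice?** Yes. Section 8.1 lets a patient continue one drug while the other is withheld, so the last dose of olaparib and the last dose of ascorbic acid need not coincide. Section 7.4.2 recognises this by timing the end-of-treatment visit from whichever last dose is later. The contraception sections have no such rule.

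**Does the follow-up window cover the commitment?** The window in 9.1.6 ends at 3 months and the criterion 12 commitment ends at 6, leaving 6 − 3 = 3 months covered by the commitment but not by that sentence. The neighbouring wording in 9.1.6 and the text in 9.5.1 would cover those months, because they refer to all pregnancies. The two sets of instructions therefore differ on whether such a conception is in scope. The reporting deadline in 9.5.1 does not settle it, because its time unit is garbled (weeks and days run together).

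**The case against.** Several points on the other side carry weight.

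- **The 1-month figure is a floor.** A man who keeps to 6 months, counted from the later last dose, satisfies every section, so no two rules are impossible to follow together. This stands. The conflict is between stated minimums, and a minimum tells the reader what is sufficient.
- **Sections 5.1 and 7.8 do not defer to Appendix C on duration.** A reader might infer that they do, because both cite it. They cite it for acceptable methods, and each states its own period for the male patient. Only their sentences on the female partner's contraception give no period of their own.
- **Conceptions in months 4 to 6 are not simply lost.** A reader might infer this from the 3-month sentence alone. The all-pregnancies wording in 9.1.6 and 9.5.1 does not support it. What remains is a mismatch between instructions.
- **Patients follow the consent form, not a protocol appendix.** A reader might infer that partners are in fact protected for different periods. The consent pages are not in the reviewed copy, so what patients are told cannot be seen. The documents show only that staff could instruct inconsistently.
- **Exposure is small.** At most 15 men are enrolled, all with testosterone below 50 ng/dL and continuing castration. The documents give no fertility figure. Conception is probably uncommon (an assumption), but the protocol imposes the safeguard even on surgically sterilised men, and Section 7.8 extends it to partners who are already pregnant.

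**Conclusion.** The inconsistency is real and should be corrected. Three minimum periods after treatment (6 months, 3 months and at least 1 month) stand in the current text, with a largest gap of 5 months and no common starting point. The 3-month conception window is 3 months shorter than the eligibility commitment and disagrees with the unlimited wording around it. The conclusion rests on the protocol text alone and assumes that none of the sections is meant to override the others; no order of precedence is stated. The documents do not show that any partner has been, or will be, under-protected, or that pregnancies would go unrecorded. This is a matter of partner and fetal safety and of clear instructions to sites. It has no effect on sample size, error rates or analysis.

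**What to change.** Reconcile criterion 12 of Section 5.1, Section 7.8, Section 9.1.6 and both statements in Appendix C to one post-treatment duration and one starting point, saying how that starting point is determined when the two drugs stop on different dates. Make the conception follow-up window in 9.1.6 cover that duration. Align it with the all-pregnancies wording in 9.1.6 and in the participating-sites part of 9.5.1, and repair the garbled reporting deadline there. Check that the consent form gives the same figure. Which duration is right is for the sponsor and its clinical and safety advisers; this review takes no position. The cost is a protocol wording amendment, plus a consent-form revision if that form carries a different figure. No change to the statistical plan is needed.

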## Acceptable Non-hormonal birth control methods include:

- Total sexual abstinence. Abstinence must continue for the total duration of study treatment and for three months after the last dose for male patients. Periodic abstinence (e.g. calendar ovulation, sympothermal, post ovulation methods) and withdrawal are not acceptable methods of contraception.
- Vasectomised sexual partner PLUS male condom with participant assurance that partner received post-vasectomy confirmation of azoospermia.
- Tubal occlusion PLUS male condom
- IUD PLUS male condom. Provided coils are copper-banded

# Acceptable hormonal methods:

- Normal and low dose combined oral pills PLUS male condom
- Cerazette (desogestrel) PLUS male condom. Cerazette is currently the only highly efficacious progesterone based pill.
- Hormonal shot or injection (eg., Depo-Provera) PLUS male condom
- Etonogestrel implants (e.g., Implanon, Norplant) PLUS male condom
- Norelgestromin / EE transdermal system PLUS male condom
- Intrauterine system [IUS] device (eg., levonorgestrel releasing IUS -Mirena®) PLUS male condom
- Intravaginal device (e.g., EE and etonogestrel) PLUS male condom

# APPENDIX D: Actions required in cases of combined increase of Aminotransferase and Total Bilirubin – Hy's Law

#### 1. INTRODUCTION

During the course of the study, the investigator will remain vigilant for increases in liver biochemistry. The investigator is responsible for determining whether a patient meets potential Hy's Law (PHL) criteria at any point during the study. The Investigator participates, together with AstraZeneca and McGuff clinical project representatives, in review and assessment of cases meeting PHL criteria to agree whether Hy's Law (HL) criteria are met. HL criteria are met if there is no alternative explanation for the elevations in liver biochemistry other than Drug Induced Liver Injury (DILI) caused by the Investigational Medicinal Product (IMP). The Investigator is responsible for recording data pertaining to PHL/HL cases and for reporting Adverse Events (AE) and Serious Adverse Events (SAE) according to the outcome of the review and assessment in line with standard safety reporting processes.

#### 2. **DEFINITIONS**

Potential Hy's Law (PHL)

- Aspartate Aminotransferase (AST) or Alanine Aminotransferase (ALT) ≥ 3x Upper Limit of Normal (ULN) and Total Bilirubin (TBL) ≥2xULN at any point during the study irrespective of an increase in Alkaline Phosphatase (ALP).
- The elevations do not have to occur at the same time or within a specified time frame.

Hy's Law (HL)

- AST or ALT  $\geq$  3x ULN and TBL  $\geq$ 2xULN, where no other reason, other than the IMP, can be found to explain the combination of increases, e.g. elevated ALP indicating cholestasis, viral hepatitis, another drug.
- The elevations do not have to occur at the same time or within a specified time frame

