# 7.4 Duration of Therapy and Criteria for Removal from Study

Patients will be removed from study when any of the criteria listed apply. The reason for study removal and the date the patient was removed must be documented in the Case Report Form.

In the absence of treatment delays due to adverse event(s), treatment may continue until one of the following criteria applies:

- Disease progression by RECIST criteria v1.1 (Appendix E) or bone progression per PCWG3 (see Section 7.4.1)
- Disease progression by symptomatic assessment
- PSA doubling from baseline value, confirmed by a second value at least 4 weeks apart, with a minimum time since initiation of therapy of 12 weeks (see **Section 7.4.1**)
- Intercurrent illness that prevents further administration of treatment
- Unacceptable adverse event(s): toxicity (defined in **Section 8.1**) that has not recovered in 2 weeks or if the same toxicity recurs at the decreased dose (unless there is strong evidence of clinical benefit to justify continuation of dosing with study treatment, and the rationale must be discussed with the Principal Investigator before a decision is made)
- The subject or legal representative (such as a parent or legal guardian) withdraws consent for treatment
- If, in the opinion of the Investigator, a change or temporal or permanent discontinuation of therapy would be in the best interest of the subject
- Patient is noncompliant with respect to taking drugs, keeping appointments, or having tests required
- for the evaluation of drug safety and efficacy Bone marrow findings consistent with myelodysplastic syndrome (MDS)/acute myeloid leukemia (AML)
- Potential Hy's Law cases (AST or ALT ≥3x ULN and TBL ≥2x ULN with no other reason)

Because an excessive rate of withdrawals can render the study uninterpretable, unnecessary withdrawal of patients should be avoided. When a patient discontinues

treatment early, the investigator should make every effort to contact the patient and to perform a final evaluation. The reasons for withdrawal should be recorded.

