# Management of non-hematological toxicity

Dose interruptions are allowed as required, for a maximum of 4 weeks. Patients who require an interruption in study drug >4 weeks due to toxicity must discontinue study drug. Where toxicity reoccurs following re-challenge with study treatment, then the patient should be considered for dose reduction or must permanently discontinue study treatment.

Olaparib can be dose reduced to 250mg bid as a first step and to 200mg bid as a second step. Treatment must be interrupted if any NCI-CTCAE grade 3 or 4 adverse event occurs which the investigator considers to be related to administration of study treatment.

Adverse events possibly related to study drug must be resolved to grade 1 or baseline prior to resumption of dosing.

**Note**: In case a patient shows an AST or ALT  $\geq 3$  ULN or total bilirubin  $\geq 2$  ULN please refer to **Appendix D** 'Actions required in cases of combined increase of Aminotransferase and Total Bilirubin – Hy's Law', for further instructions. Potential Hy's Law cases (AST or ALT  $\geq 3x$  ULN and TBL  $\geq 2x$ ULN with no other reason) must discontinue the study.

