# 13.6 Futility and Safety Monitoring Plan

Given the small number of patients and the importance of obtaining correlative data to consider during the final evaluation of the study results, there will be no futility monitoring for efficacy during this pilot study. The trial will however employ a standard safety monitoring plan for adverse events. In addition, if any patient is diagnosed with an adverse event of special interest: myelodysplastic syndrome, acute myeloid leukemia, new primary malignancy (other than MDS/AML) or pneumonitis during the trial, the trial will be paused for a safety review.

Toxicity will be monitored continuously for grade 3-4 adverse events that do not resolve to grade 2 following four-weeks drug discontinuation (per section 8.1). The stopping rule is based on the posterior probability that the combination of treatments is too toxic. If the rate of these toxicities convincingly exceeds 30%, the study PI will hold enrollment if the posterior probability of risk greater than 0.30 is 65% or higher. The prior for this toxicity monitoring rule is beta (2,6). This corresponds to assuming our prior guess for the toxicity rate is 25%, and there is 90% probability that this proportion is between 5% and 52%.

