## 5. REVIEW AND ASSESSMENT OF POTENTIAL HY'S LAW CASES

The instructions in this Section should be followed for all cases where PHL criteria are met. No later than 3 weeks after the biochemistry abnormality was initially detected, the Study Physician contacts the Investigator in order to review available data and agree on whether there is an alternative explanation for meeting PHL criteria other than DILI caused by the IMP. The AstraZeneca Medical Science Director and Global Safety Physician will also be involved in this review together with other subject matter experts as appropriate. According to the outcome of the review and assessment, the Investigator will follow the instructions below.

If there is an agreed alternative explanation for the ALT or AST and TBL elevations, a determination of whether the alternative explanation is an AE will be made and subsequently whether the AE meets the criteria for an SAE:

• If the alternative explanation is not an AE, record the alternative explanation on the appropriate CRF

• If the alternative explanation is an AE/SAE, record the AE/SAE in the CRF accordingly and follow the AZ standard processes

If it is agreed that there is no explanation that would explain the ALT or AST and TBL elevations other than the IMP:

- Report an SAE (report term 'Hy's Law') according to AstraZeneca standard processes.
  - The 'Medically Important' serious criterion should be used if no other serious criteria apply
  - As there is no alternative explanation for the HL case, a causality assessment of 'related' should be assigned

If there is an unavoidable delay of over 3 weeks in obtaining the information necessary to assess whether or not the case meets the criteria for HL, then it is assessed that there is no alternative explanation until such time as an informed decision can be made:

- Report an SAE (report term 'Potential Hy's Law') applying serious criteria and causality assessment as per above
- Continue follow-up and review according to agreed plan. Once the necessary supplementary information is obtained, repeat the review and assessment to determine whether HL criteria are met. Update the SAE report according to the outcome of the review

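### Section 13.6 counts a Hy's Law case only if it is grade 3-4 and unresolved after four weeks off drug, so a confirmed drug-caused case that settles sooner removes the patient but adds nothing to the toxicity rule

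*Combined protocol and SAP*

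**What the plan says.** **Patient level.** Appendix D Section 2 defines Hy's Law by AST or ALT at least 3 times, and total bilirubin at least 2 times, the upper limit of normal, "where no other reason, other than the IMP, can be found to explain the combination of increases". No CTCAE grade enters the definition. Section 7.4 lists among the removal criteria "Potential Hy's Law cases (AST or ALT ≥3x ULN and TBL ≥2x ULN with no other reason", and the non-hematological part of Section 8.2.2.3 says that such patients, "with no other reason) must discontinue the study". Neither place makes an exception for recovery.

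**Causality.** Appendix D Section 5 covers the agreed case: "If it is agreed that there is no explanation that would explain the ALT or AST and TBL elevations other than the IMP". It is reported as a serious adverse event, and "a causality assessment of 'related' should be assigned". If the review cannot be completed within 3 weeks, the case is reported on the same terms for the time being, and the assessment is repeated when the information arrives.

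**Trial level.** Section 13.6 states: "Toxicity will be monitored continuously for grade 3-4 adverse events that do not resolve to grade 2 following four-weeks drug discontinuation". It holds enrolment when the posterior probability that the risk exceeds 0.30 reaches 65%, under a beta(2,6) prior. A separate list pauses the trial after a single case: "myelodysplastic syndrome, acute myeloid leukemia, new primary malignancy (other than MDS/AML) or pneumonitis during the trial, the trial will be paused". Hy's Law is not on it. The section also says: "The trial will however employ a standard safety monitoring plan for adverse events".

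**The concern.** The four-week test in Section 13.6 refers to Section 8.1. There, a toxicity that keeps a patient off drug for more than four weeks leads to permanent discontinuation unless an exemption is granted. In that setting persistence is a reasonable marker of a toxicity that costs the patient the treatment.

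Hy's Law reaches permanent removal by another route. The patient is removed because of the diagnosis, and recovery does not bring him back. A filter based on persistence therefore gives zero to a removal that the protocol itself attributes to the drug, provided the liver values settle within four weeks.

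Section 4.2.8 says that the two agents have not been combined before in this disease. The posterior rule is the only pre-specified quantitative safety boundary. If it omits some drug-caused permanent removals, the rate compared with 30% is lower than the rate a reader would take it to be.

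**Working it through.** **Inputs.** Prior beta(2,6), risk limit 0.30 and cut-off 0.65 (Section 13.6); boundary (Table 9); operating characteristics (Table 10); 12 patients (Section 13.5 and the last column of Table 9).

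**Formula.** After s counted events in n patients the posterior is beta(2+s, 6+n-s). For whole-number parameters, P(risk > 0.30) = P(X ≤ 1+s), where X is binomial with 7+n trials and probability 0.30.

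**Step 1: reproduce the plan.** The smallest s that reaches 0.65 is 2 at n = 2, 3 at n = 3-6, 4 at n = 7-9 and 5 at n = 10-12. This is Table 9 exactly (2 events in 3 patients gives 0.6496, just short). Exact recursion over 12 patients gives:

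| Event risk | 0.15 | 0.25 | 0.30 | 0.35 | 0.40 | 0.45 | 0.50 |
|---|---|---|---|---|---|---|---|
| Table 10, % stopped | 7.4 | 26.5 | 39.8 | 52.3 | 67.8 | 78.6 | 86.3 |
| Exact, % stopped | 7.6 | 26.9 | 40.0 | 53.6 | 66.5 | 77.5 | 86.1 |

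All agree within 2 points, as expected of 5000 simulations. The rule is computed correctly; the question is only what it counts.

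**Step 2: which Hy's Law cases count.**

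- Grade 3-4 and not back to grade 2 after four weeks off drug: counted. Section 13.6 excludes no type of event.
- Grade 3-4 and back to grade 2 within four weeks: not counted, although the patient is removed and an agreed case is a related serious event.
- Below grade 3: would not be counted. The documents give no CTCAE liver cut-offs, so whether such cases arise cannot be settled from them, and nothing below depends on it.

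**Step 3: effect on the posterior.** These are illustrations; the documents give no Hy's Law rate.

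- Two agreed cases in the first two patients, both settling within four weeks. Uncounted (0 of 2), beta(2,8): 0.7^9 + 9 × 0.3 × 0.7^8 = 0.0404 + 0.1556 = 0.196, so enrolment continues. Counted (2 of 2), beta(4,6): P(X ≤ 3) with 9 trials = 0.730, above 0.65, so enrolment is held.
- Five such cases in 12 patients with no other counted event: 0.010 uncounted, 0.666 counted (hold).

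**Step 4: effect on the chance of a hold.** Let c be the share of Hy's Law cases that already qualify. It is unknown, so the range is 0 to 1. Assume other qualifying toxicity in 15% of patients and Hy's Law in a further 10%. The counted risk is then 0.15 + 0.10c:

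| c | 0 | 0.25 | 0.5 | 0.75 | 1 |
|---|---|---|---|---|---|
| Chance of hold, % | 7.6 | 11.3 | 15.8 | 21.0 | 26.9 |

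Counting every case moves the trial from the column for its true c to the last column. If counting instead added 5 points to the event risk (also assumed), the chance of a hold would go from 2.6% to 7.6% at a starting risk of 10%, from 7.6% to 15.8% at 15%, from 15.8% to 26.9% at 20%, and from 26.9% to 40.0% at 25%.

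**The case against.** **Other oversight exists.** Under Appendix D Sections 4 and 5, a potential case is notified to both companies and reviewed with their safety physicians. Section 9.5.1 requires serious events to be reported within 24 hours, and Section 9.4 provides an expedited report to investigators if a related event is unexpected. Sections 12.2 and 12.3 add safety meetings and Safety Monitoring Committee oversight. This stands, and it rules out a stronger reading: a reader might infer that a Hy's Law case has no trial-level consequence, and these sections show otherwise. What they lack is a pre-specified count or pause.

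**The rule does count some cases.** A reader might also infer that Section 13.6 ignores Hy's Law altogether, so that repeated cases could never move it. The text does not support that, because a persistent grade 3-4 case is a safety event like any other. In the Step 4 scenario, Hy's Law leaves the rule untouched only at c = 0.

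**The grade argument is open.** One might claim that cases below grade 3 can never count. The documents do not give the liver grades, and Section 9.3.2 describes grade 3 as including medically significant events, so an investigator might grade an agreed case 3. The point should rest on recovery within four weeks alone.

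**It is a design choice.** The rule targets toxicity that does not resolve, the pause list matches the olaparib events of special interest in Section 9.1.3, and other events that end treatment and may be transient, such as febrile neutropenia (Table 8), raise the same question. This has weight, and the sponsor may wish to consider those events too. Hy's Law differs in that the protocol already adjudicates it formally and fixes its causality as related.

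**The 30% limit was set for persistent events.** This is fair: adding recovered cases changes what the rate means, so the event definition has to be restated.

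**Conclusion.** The concern holds in a limited form. A Hy's Law case agreed to be drug-caused, but back to grade 2 within four weeks off drug, is not a safety event under Section 13.6 and triggers no pause, although the same protocol removes the patient permanently and classes the event as serious and related.

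The conclusion about which cases count rests on the text alone. Its practical size does not: the Hy's Law rate and the share settling within four weeks are both unknown. The 0.196 versus 0.730 contrast is a worst case showing that the definition can decide whether enrolment is held; it is not a forecast. The plan has no numerical error here, since Table 9 reproduces exactly and Table 10 within simulation error. This is a gap in the event definition that should be closed, not a failure of the boundary.

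**What to change.** Reconcile Section 13.6 with Sections 7.4 and 8.2.2.3 and Appendix D Section 5 by adding to 13.6, in substance: *A case agreed to be Hy's Law under Appendix D Section 5 counts as a safety event in the Table 9 rule whatever its recovery. A case still unresolved at the end of that review counts provisionally, and is removed from the count if the repeat review finds another cause.*

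Restate the event definition behind the 30% limit to include these cases. Table 9, the prior and the 65% cut-off can stay. Table 10 is indexed by event risk and so remains valid, read against the wider definition.

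The change needs no new data, because Appendix D already collects the adjudication, and it alters no patient's treatment. The cost is a higher chance of an enrolment hold, of a size that depends on the unknown Hy's Law rate. In the assumed move from 25% to 30% event risk, the rise is 40.0 - 26.9 = 13.1 percentage points, which the sponsor should accept knowingly.
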